Justice Resource Institute Institutional Review Board Protocol Changes to Research 2008-06

- 1. Date of this submission or revision: 12/09/2011
- 2. Title of Study: Application of Neurofeedback as a Mechanism of Affect Regulation Treatment of Adults with Complex Adaptation to Chronic Interpersonal Trauma Exposure
- 3. JRI IRB Code Number Assigned (contact IRB Chair): 2008-006

4. Principal Investigator Information:

Name/Degree: [name], M.D. Address: [name] [contact] [name] Email: [contact] License: Medical – Psychiatry specialization Affiliation: Trauma Center at JRI

Names/Titles of Members of Research Team:

[name], M.D., Project Director & Principal Investigator. [name]., Project Coordinator. [name], Psy.D., Project Supervisor. [name]., Project Supervisor. [name]., Interventionist. [name], B. A., Interventionist, Study Technician.

- 5. Location(s) of Study: Trauma Center at [name]
- 6. Starting Date and expected total duration of study: 12/12/2011-9/1/2012
- 7. Number of subjects to be studied: Our aim is to enroll 40 individuals with 20 assigned to the active treatment group and 20 assigned to a waitlist control group.
- 8. Relevant characteristics of subjects: (gender, age, ethnic/socioeconomic background; if individuals served by JRI (current or former) or their relatives, or if employees of JRI, specify which programs)

The initial year included 23 individuals with 20 enrolled in the study. Of those 20, 3 were men and 17 were women ranging in ages from 27-59. During year two, we enrolled 24 out of 36 individuals screened (16 females, and 8 males between the ages of 32 and 62). 16 completed the study. During year three, we aim to enroll the majority of participants from the active client pool at the Trauma Center and expand to other agencies as necessary (i.e. enrollment targets are not met in a timely manner).

9. Expected period of study for each individual subject: Participants will be asked to commit to 12 weeks of twice-weekly 30 minute sessions in addition to assessments at

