Year 2 represented a more controlled trial. During this time, sensor placement and procedures have been protocolized. Additionally, assessments were administered at standardized points. This permitted more in-depth analyses of change over the course of treatment. We have found a statistically (although not yet clinically) significant drop in total PTSD symptoms as measured by the Davidson Trauma Scale (time 1 = 70.96, time 40 = 54.77; pr2 = .21). Additionally, we have found significant drops on the Affect Dysregulation subscale of the Inventory of Altered Self-Capacities (time 1 = 24.33, time 40 = 16.82; pr2 = .56). In an effort to understand more about the mechanisms of neurofeedback, we performed multilevel mediation analyses testing whether PTSD symptom change mediated affect dysregulation or vice-versa. We found that the model with affect dysregulation mediating PTSD symptom change is a much better fit, resulting in a 93% mediation.

Study Design

General Study Design.

The proposed year three pilot study continues to be exploratory in nature; however, we are adding a waitlist control group, reducing the number of sessions, consolidating to a single sensor placement, changing inclusion criteria, and adding assessment measures. Thus, the overall study design will be as follows: 1) potential participants will be screened via a telephone interview. This interview will assess whether participants will meet the initial inclusion criteria for the study. 2) Participants who meet initial eligibility requirements will be scheduled for an in-person assessment. During this meeting, participants will be briefed on the study, study technicians will assess understanding of consent, and the participant will indicate consent by signing the form. 3) Participants will complete baseline assessments. During the baseline assessment appointment, participants will be excluded from the study if they a) do not meet criteria for PTSD based on their CAPS Diagnostic Interview or b) receive a score of 40 or higher on the DES. 4) Participants will be randomly assigned to either waitlist control or active treatment. 5) Participants assigned to active treatment will be scheduled with the study technician for twice weekly appointments. Participants assigned to the waitlist will be given information on completing assessments. 6) At the conclusion of treatment (or waitlist period), participants will complete the termination assessment and receive compensation. 7)

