Participants will receive auditory and visual feedback indicating reward. Feedback (reinforcement) is provided by means of beeps and simple computer games. During the training, the reward condition is either extended or removed based on the degree to which the amplitude of the measured EEG activity in the targeted spectral bands meets or fails to meet the training parameters or goals. The reinforcement used for operant conditioning is earning more beeps and advancing the computer game. We will use the EEGer neurofeedback system manufactured by EEG Spectrum International.

Control Group

We propose to enroll a cohort of 20 individuals who will provide a *waitlist* control against which to compare the results obtained from the neurofeedback group. The control group will consist of individuals receiving individual psychotherapy services at the Trauma Center or other community agencies. Maintenance of ongoing, weekly psychotherapy will be a requirement for participation. Waitlist participants will be asked to complete the same measures at the same time points as individuals in the active treatment. Overall, participants in the control group will complete a baseline assessment, six interim assessments, and the termination assessment along the same timeline as those in the active treatment condition. Participants for the control will be randomly selected and all waitlist participants will be offered the active treatment at the end of the waitlist period. Once these participants begin receiving neurofeedback, they will follow the same assessment time-line as the original active treatment group by being assessed at midtreatment, post-treatment and one-month follow up.

Participant Information

Description of the methods to be used to assure informed consent of each participant prior to participation. All adults interested in receiving neurofeedback (NFB) services at the Trauma Center (or other clinics and agencies to which we open inclusion) will be invited to be screened for participation in this study on the role of NFB as a method of affect regulation in the treatment of adults with complex adaptation to chronic interpersonal trauma exposure. Prior to the screening, potential participants will be provided a detailed verbal description of the study. The initial screening will take place

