The modeling flexibility and power of the multilevel regression approach makes it very well suited to test all of the study's hypotheses. To test PTSD symptom change, two different types of analyses will be conducted. First, the administration of the DTS on several occasions from the baseline assessment, during treatment, and throughout the follow-up period will allow us to capitalize on the advantages of contemporary growth curve approaches that produce very efficient estimates of change over time and increased power to detect differences across treatment conditions (as power is a function of both sample size and number of assessments). Therefore, growth curve analyses will be conducted from a multilevel regression framework to evaluate change over time in PTSD symptoms as assessed by the DTS and how change over time differs as a function of treatment condition [19].

To supplement these analyses and document group differences in change over time on the CAPS, which will only be administered on four occasions (pre-, mid-, post-treatment, and follow-up), analyses with time modeled as a categorical variable (via a set of dummy coded variables) will be conducted. This approach is analogous to conducting a repeated measures ANOVA that capitalizes on the numerous benefits of the multilevel regression approach.

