Procedures for protecting participants' confidentiality: For study purposes, all data will be de-identified and a numeric coding system and a numeric coding system has been put in place. All data entered into study databases are identified by this numeric system only.

Name of funding/granting agency, and annual and total budget amount: Total initial 3-year funding award =\$493,760. Total expended in Y01= \$140,046. Total to be expended in Y02 ~ \$160,000. Estimated remaining balance to conduct Y03 project ~ \$193,000. Foundation has verbally agreed to increase amount and duration of final year of award as necessary to ensure successful conduct of project as delineated above.

Anticipated final product: The anticipated final products for this evaluation will include the following: 1) most importantly we aim to show proof-of-concept by demonstrating a

statistically and clinically significant improvement in reported symptoms of participants which will be suitable for publication in scholarly journals, 2) delineation of specific protocols, guidelines, sequences and/or clinical decision-making strategies regarding application of NFB with complexly traumatized adults; 3) compilation of written narrative case studies to illustrate NFB adaptation process and provide descriptive outcomes derived from NFB application; and 4) grant applications for further controlled trials of NFB.

Signature of Principal Investigator:

hund

Citations

- 1. Rauch, S.L., et al., *A Symptom Provocation Study of Posttraumatic Stress Disorder Using Positron Emission Tomography and Script-Driven Imagery*. Archives of General Psychiatry, 1996. **53**: p. 380-387.
- 2. Lanius, R.A., et al., *Brain activation during script-driven imagery induced dissociative responses in PTSD: A functional magnetic resonance imaging investigation.* Biological Psychiatry, 2002. **52**(4): p. 305-311.
- 3. Georgopoulos, A.P., Tan, H-R.M., Lewis, S.M., Leuthold, A.C., Winskowski, A.M., Lynch, J.K. et al., *The synchronous neural interactions test as a functional neuromarker for post-traumatic stress disorder (PTSD): a robust classification method based on the bootstrap* Journal of Neural Engineering, 2010. 7(1): p. 1-7.

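### The protocol's leading aim lets proof-of-concept be claimed from improvement in participants, without tying it to the waitlist comparison the protocol plans

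*Protocol*

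**What the plan says.** The section Anticipated final product lists four products. The first opens "most importantly we aim to show proof-of-concept by demonstrating a" and continues "statistically and clinically significant improvement in reported symptoms of participants". It gives no comparator, and the protocol nowhere else says what result would count as treatment success.

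The design is controlled. Item 7 states: "Our aim is to enroll 40 individuals with 20 assigned to the active treatment group and 20 assigned to a waitlist control group". The Control Group section describes the waitlist as a "control against which to compare the results obtained from the neurofeedback group".

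The Data Analysis Plan uses that control. Its first PTSD analysis is a growth-curve model of the DTS that examines "how change over time differs as a function of treatment condition". A second analysis, described as a supplement, is meant to "document group differences in change over time on the CAPS".

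Two features of the population also bear on the point. General Study Design excludes anyone who does not meet PTSD criteria on the baseline CAPS. The Control Group section adds: "Maintenance of ongoing, weekly psychotherapy will be a requirement for participation". The Inclusion Criteria require weekly psychotherapy of all participants.

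**The concern.** The design and analysis ask whether people on neurofeedback improve more than people on the waitlist. The leading aim asks only whether participants improve. These are different questions, and the second can be answered yes when the first is answered no.

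In this trial symptoms could fall for reasons other than neurofeedback. Everyone is selected for current PTSD on an interview score, so some regression to the mean is to be expected. Everyone also stays in weekly psychotherapy, and the measures are repeated. Both arms share these influences, so the arm comparison removes them and a before-after comparison does not.

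What is at stake is the wording of the conclusion. If both arms improved equally, the stated aim could still be described as met in its statistical part, while the planned analysis found nothing. The same section expects publications and further grant applications to follow.

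**Working it through.** The protocol gives no alpha, power, effect size, SD or expected waitlist change, so there is no stated figure to reproduce. The check asks how often each kind of test is significant when neurofeedback adds nothing.

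**Inputs from the protocol**
- 20 per arm (item 7).
- Year 2 DTS change, from a cohort studied before the waitlist was added: "time 1 = 70.96, time 40 = 54.77; pr2 = .21" (Preliminary results). The drop is 70.96 − 54.77 = 16.19 points, or 16.19/70.96 = 22.8%.
- Year 2 numbers: 24 enrolled, 16 completed (item 8).

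**Assumptions**
- Two-sided alpha 0.05.
- The same standardised change dz (mean change divided by the SD of change) in both arms, so the true neurofeedback effect is zero.
- A simple before-after or change-score t-test stands in for the planned multilevel models.

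**Step 1. A reference point for dz.** Convert the Year 2 partial r² with t = √(pr2 × df / (1 − pr2)) and dz = t/√(df + 1). The protocol does not give the df, so both Year 2 counts are tried.
- df = 15: t = √(0.21 × 15/0.79) = 2.00; dz = 2.00/√16 = 0.50.
- df = 23: t = √(0.21 × 23/0.79) = 2.47; dz = 2.47/√24 = 0.50.

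This is the total uncontrolled change, including anything neurofeedback did. It therefore serves as the top of an illustrative range and does not estimate the non-specific part. The range used is 0.2 to 0.5.

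**Step 2. Before-after test in the 20 treated people.** The probability of significant improvement is 1 − F(t₀.₉₇₅,₁₉), where F is the noncentral t distribution with 19 df and noncentrality dz × √20.

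| Shared change dz | Noncentrality | Probability of significant improvement |
|---|---|---|
| 0.2 | 0.89 | 13.3% |
| 0.3 | 1.34 | 24.6% |
| 0.4 | 1.79 | 39.7% |
| 0.5 | 2.24 | 56.4% |

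Counting rejections in either direction gives 13.6% at 0.2 and 56.5% at 0.5, practically the same.

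**Step 3. Arm comparison of change, 20 against 20.** A shared change cancels, so the noncentrality is 0 whatever dz is. The test rejects 5% of the time, and 2.5% of the time in favour of neurofeedback. A simulation of 40,000 trials per setting agrees. At dz = 0.5 the before-after test showed significant improvement in 56.3% of runs. The arm comparison rejected in 5.0%, with 2.6% favouring neurofeedback.

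**The case against.** The strongest reply is that this is a sentence in a list of deliverables and not a decision rule. The list sits beside the budget and also promises case narratives. Both PTSD analyses in the Data Analysis Plan already compare the arms, and General Study Design calls the year-three study an exploratory pilot. Read with those sections, improvement could simply mean improvement as analysed there. Much of this stands, and it limits the point to wording. It does not remove it: the sentence is the only statement of success, it is ranked first, and nothing in it refers to the planned comparison.

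A reader might infer several stronger things that the documents do not support.

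- *That no controlled test of PTSD change is planned.* Two are planned. The gap is only that the aim is not linked to them.
- *That 56% is the chance of a false proof-of-concept.* The aim requires clinical as well as statistical significance. Preliminary results describes the Year 2 drop, the source of the 0.5, as statistically but not yet clinically significant. A change of that size might therefore fail the full criterion.
- *That before-after data from all 40 people would be pooled after crossover.* No section plans such an analysis, and the section on remuneration treats neurofeedback after the waitlist as optional.
- *That the uncontrolled Year 2 result is the reason for adding a waitlist.* General Study Design reports the addition and gives no reason.
- *That the protocol fails to rank its PTSD measures.* The DTS analysis comes first and the CAPS is its supplement. Formal naming of a primary endpoint may be left to the SAP.

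**Conclusion.** The point holds as a mismatch of moderate weight between the leading aim and the protocol's own design and analysis. Taken literally, the statistical half of the aim can be met by improvement that both arms share. With an assumed shared change of 0.2 to 0.5 SD, 20 treated people and two-sided alpha 0.05, that happens about 13% to 56% of the time. The arm comparison would favour neurofeedback in 2.5%.

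The figures are illustrative. They rest on an assumed dz range, an assumed alpha, unstated df for the Year 2 partial r² and a simplified test. They also leave out the clinical-significance requirement, whose threshold the protocol does not give. The conclusion that the aim names no comparator does not depend on them.

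**What to change.** Reword product 1 along these lines: *proof-of-concept is shown if PTSD symptoms improve more on active neurofeedback than on waitlist from baseline to post-treatment, judged by the DTS condition-by-time analysis, with the CAPS analysis as supplement; changes within an arm, and changes after waitlist participants start neurofeedback, are descriptive.* The clinical-significance requirement can stay alongside.

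This takes one sentence and needs no new participants, visits, measures or analyses. The price is a stricter claim. In a simple two-sample comparison of change with 20 per arm and two-sided alpha 0.05, power is about 34% for a true difference of 0.5 SD of change, 69% for 0.8 and 80% for 0.91. The planned growth-curve model may do better by using more assessments. A null arm comparison would then leave proof-of-concept unshown, even if the treated group had improved.
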